5.2 Research design process

5.2.1 Study the specific implementation process

1. Phase One: Screening and enrolling the population

- i. Conduct ethical reviews and clinical research protocol reviews for the project;
- ii. It is planned to select 500 patients with malignant solid tumors, collect their basic information and sign the "Informed Consent Form".
- iii: It is planned to select 500 healthy subjects and collect basic information.

2. Phase Two: Collect blood samples for serum histone succinylation detection

[figure not shown]
Blood samples were collected from all 500 enrolled individuals and 500 healthy subjects who met the requirements for serum histone succinylation detection.

3. Phase Three: Statistical analysis of Screening Results

- i. Western blot was used to evaluate the differences in serum histone succinylation between malignant solid tumors and healthy individuals to verify its early screening value.

ii. Statistically analyze the correlation between serum histone succinylation and tumor efficacy (including surgical treatment, radiotherapy, and systemic therapy) as well as clinicopathology. The therapeutic effect was evaluated using RECIST1.1 criteria.

5.2.2 Research flowchart

5.2.3 Blood collection process table

grouping								
	Screening period							
healthy person	D-7—D0							
Cancer patients are receiving systemic treatment		Chemotherapy cycle						
		C1D1	C2	C3	C4	C5	C6	
	D-7—D0			D1± 3		D1±3		
Cancer patients who receive radical chemoradiotherapy/radiotherapy	D-7—D0	After the completion of radiotherapy/chemoradiotherapy		Four to six weeks after the completion of radiotherapy/chemoradiotherapy				
		D _{end} D _{end} +3		On the day of follow-up				
A tumor patient undergoing surgery	D-7—D0	postoperation	Postoperative discharge day/the day before discharge					
	D1—D3							

5.3 statistic analysis

This study adopted a mismatched case-control study (500 cases in the case group and 500 cases in the healthy control group). The sample size was determined based on the effect size of the previous pre-experiment (Cohen's $d=1.2$) and considering a 10% dropout rate. All statistical analyses were performed using R, with a test level of $\alpha=0.05$. Main analysis 1) Comparison of histone succinylation levels between groups - After Shapiro-Wilk normality and Levene homogeneity of variance tests, independent sample t-tests (conforming to normal distribution) or Mann-Whitney U tests (non-normal data) were selected. Report mean difference (MD)/median difference and 95% confidence interval (CI), Cohen's d effect size; 2) Diagnostic

efficacy evaluation - Calculate the area under the curve (AUC) and its Bootstrap 95% CI through the ROC curve, and determine the optimal cut-off value by maximizing the Youden index. And calculate the sensitivity, specificity, positive predictive value (PPV), negative predictive value (NPV), and their exact Clopper-Pearson 95% CI. Secondary analysis: 1) Subgroup correlation - One-way analysis of variance (ANOVA) or Kruskal-Wallis test was used to compare the level differences among different tumor types (Bonferroni-adjusted post hoc test), and Cuzick's trend test was used to analyze the ordered association of TNM stages; 2) Therapeutic effect evaluation - The level changes before and after treatment were evaluated using paired t-test /Wilcoxon signed-rank test; 3) Prognostic value - The baseline succinylation level (median grouping) was included in the Cox proportional hazards model. After adjusting for age, stage, and treatment regimen, the hazard ratio (HR) and 95% confidence interval (CI) were calculated. The survival curve was plotted using the Kaplan-Meier method (Log-rank test). Multivariate analysis: A Logistic regression model was constructed (including succinylation level and covariates such as age and gender). AUC was compared by DeLong test, goodness-of-fit was evaluated by Hosmer-Lemeshow calibration curve, and clinical net benefit was analyzed by decision curve (DCA). If multi-site modifications are detected, LASSO regression is used to screen biomarker combinations. Quality control: Grubbs test /Winsorize for outliers, multiple imputation (MICE) for filling <5% of missing covariates. Sensitivity analysis: Robustness was verified by excluding stage I tumors, and the 70%-30% dataset was split for cutoff value training - validation. All multiple comparisons were controlled for the false discovery rate (FDR) using the Benjamini-Hochberg method.

六、Ethical requirements

Clinical research will comply with relevant regulations such as the Declaration of Helsinki of the World Medical Congress. The research can only be implemented after it has been approved by the ethics committee before it commences.

Before each subject is enrolled in this study, the researcher is responsible for providing the subject or their agent with a complete and comprehensive introduction

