2.2 Risk/Benefit assessment

risk assessment:

This study was an observational one, and the core intervention was only a single venous blood sample collection of 3mL (approximately 1ml of serum). This operation

is a routine and mature medical practice in clinical practice, with extremely low and controllable risks.

Benefit evaluation:

Cancer patients: They will not receive immediate individualized diagnosis or treatment recommendations from this study. However, the data it contributes will drive the development of better tumor markers, which may benefit its future disease management (such as more precise follow-up monitoring).

Healthy control subjects: Contribute to establishing baseline standard values for healthy populations and promote public health. After the research is completed and the method is mature, the baseline data in which it participated may provide a reference background for its own future similar screening.

三、 Research objectives and endpoints

3.1 objective

3.1.1 main purpose

To evaluate the differences in serum histone succinylation between malignant solid tumors and healthy individuals, in order to verify its early screening value.

3.1.2 secondary objective

To clarify the correlation between histone succinylation modification in serum and different types of tumors and tumor stages, and to statistically analyze the correlation between histone succinylation in serum and therapeutic effects (including surgical treatment, radiotherapy, and systemic therapy) as well as clinicopathology.

3.2 evaluation index

The evaluation indicators are: the sensitivity, specificity, positive predictive value, negative predictive value of the serum histone succinylation screening method, and the predictive value of the Youden index (early diagnosis, therapeutic effect evaluation and prognosis).

四、 study population

4.1 inclusion criteria

case group

- 1) ≥ 18 years old, gender not limited;
- 2) Malignant solid tumors diagnosed by cytology or histology require subsequent anti-tumor treatment (systemic therapy, radical or concurrent chemoradiotherapy/radiotherapy, or surgical treatment).

control group

- 1) ≥ 18 years old, gender not limited;
- 2) Non-tumor patients undergoing health check-ups;

4.2 exclusion criteria

- 1) Pregnant women
- 2) Those with severe mental disorders or language communication disorders;
- 3) Other circumstances where the researcher deems it unsuitable to participate in this study.

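### Both main case-control analyses are unadjusted although the groups are unmatched, so age or sex differences can bias the headline difference and AUC in either direction.

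*Protocol*

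**What the plan says.** Protocol section 5.3 describes the design: "This study adopted a mismatched case-control study", with 500 cases and 500 healthy controls. The only sensible reading of the adjective is unmatched. Section 4.1 requires both groups to be 18 or over, of either sex, and defines controls as "Non-tumor patients undergoing health check-ups". No matching, frequency matching or quota on age or sex is described. The line after the exclusion criteria in section 4.2, saying that controls are treated like cases, concerns those criteria and is not a matching rule.

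Section 5.3 then names two main analyses:

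- **Group comparison.** After checks of normality and variance, "independent sample t-tests (conforming to normal distribution) or Mann-Whitney U tests (non-normal data) were selected", reported with a mean or median difference and Cohen's d.
- **Diagnostic performance.** "Calculate the area under the curve (AUC) and its Bootstrap 95% CI through the ROC curve", followed by a Youden cut-off with sensitivity, specificity, PPV and NPV.

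Neither has a covariate. Age and sex enter the case-control contrast only later, under multivariate analysis: "A Logistic regression model was constructed (including succinylation level and covariates such as age and gender", with a DeLong comparison of AUCs. The Cox model also adjusts for age, but it concerns prognosis. The sensitivity analyses (excluding stage I; a 70/30 split) do not address confounding.

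**The concern.** The primary objective in section 3.1.1 is the difference between tumour patients and healthy people, read as evidence of early screening value. If the groups differ in age or sex, and the marker varies with either, the crude difference mixes a demographic effect with any tumour effect. The crude AUC and cut-off carry the same mixture, and they reflect the age mix of this sample, not that of a population to be screened.

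The groups are large, so a small bias is enough to move the test. With 500 per group, a standardised difference of about 0.18 is detected with 80% power. The main result could then be significant, or missed, for reasons unrelated to tumour.

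This is not a detail left to a later analysis plan. The protocol itself names the main analyses and fixes them as unadjusted.

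**Working it through.** **The plan's own figure.** Section 5.3 attributes the sample size to d = 1.2 with 10% dropout. It does not state power or sidedness. Two-sided alpha 0.05 and 80% power give n = 2(1.960 + 0.842)²/1.2² = 10.9, so 11 per group, or 11/0.9 = 12.2, so 13, with dropout. At 90% power the figures are 15 and 17. The stated 500 is not reproduced. That is a separate matter, and this point does not depend on it. What matters here is the smallest effect that 500 per group detects with 80% power: (1.960 + 0.842) × √(2/500) = 0.177. At 450 per group (500 less 10%) it is 0.187.

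**Inputs for the bias.** From the protocol: 500 per group, alpha 0.05 (taken as two-sided), no covariates. Assumed, because the protocol gives neither: the age gap g between groups in within-group SDs, and the within-group marker-age correlation r. No true tumour effect is assumed, and r and g have the same sign.

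**Formulae.** Spurious standardised difference d = r × g. Noncentrality = d/√(2/500) = d/0.0632. Rejection rate = Φ(ncp − 1.96) + Φ(−ncp − 1.96). AUC = Φ(d/√2).

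| r | g | d | ncp | Rejection | AUC |
|---|---|---|---|---|---|
| 0.1 | 0.5 | 0.05 | 0.79 | 12.4% | 0.514 |
| 0.1 | 0.8 | 0.08 | 1.26 | 24% | 0.523 |
| 0.2 | 0.5 | 0.10 | 1.58 | 35.3% | 0.528 |
| 0.2 | 0.8 | 0.16 | 2.53 | 71.6% | 0.545 |
| 0.3 | 0.5 | 0.15 | 2.37 | 66.0% | 0.542 |
| 0.3 | 0.8 | 0.24 | 3.79 | 96.7% | 0.567 |

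The correct values with no tumour effect are 5% and 0.500. If r and g have opposite signs, d is negative. A true tumour-related increase would then be partly masked.

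**Simulation check**, 450 per group, no tumour effect (2,000 runs; 500 for the logistic model and for the combined and age-alone AUCs):

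| Quantity | r = 0.2, g = 0.5 | r = 0.2, g = 1 |
|---|---|---|
| t-test rejects | 31.8% | 84.6% |
| Mann-Whitney rejects | 30.6% | 83.2% |
| Linear regression with age rejects | 4.9% | 5.0% |
| Marker term in logistic model with age rejects | 5.2% | 4.8% |
| AUC, marker alone | 0.528 | 0.557 |
| AUC, age alone | 0.639 | 0.762 |
| AUC, marker + age | 0.640 | 0.763 |

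Both adjusted tests hold the nominal level. The combined AUC, however, is almost entirely age.

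**Sex alone**, 450 per group: if the marker differs by 0.2 to 0.4 SD between the sexes and the sex share differs by 10 to 30 points between groups, d = 0.02 to 0.12 and the crude test rejects in 6% to 44% of studies.

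**Against the planned effect.** d = 1.2 corresponds to AUC = Φ(1.2/√2) = 0.80. Removing 0.05 to 0.24 SD leaves d = 1.15 to 0.96 and AUC 0.79 to 0.75.

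**The case against.** The strongest reply is that the protocol already plans an adjusted analysis. In an unmatched case-control study, the marker coefficient in a logistic model with age and gender is a standard test of association given those covariates, and the simulation confirms its error rate. This stands, and it rules out the inference that the plan has no valid adjusted test. Part of the issue is which analysis is called main. What remains is that the headline difference, Cohen's d, AUC, cut-off, sensitivity and specificity are all crude. In addition, the protocol does not say which two AUCs the DeLong test compares. If it sets the marker alone against the full model, age by itself can produce the gain.

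A reader might also infer that any weak marker-age relation will make the main test significant, or that the AUC will be inflated. Neither is supported. At r = 0.1 the table gives 12% to 24%, so most such studies would not be significant. The direction depends on signs that the documents do not give.

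Finally, if the true effect is near d = 1.2, modest confounding would not change significance and would move the AUC by only 0.01 to 0.05. That is fair. However, the pilot listing in section 2.1.3 gives no ages or sexes, so it cannot show that 1.2 is itself free of confounding.

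**Conclusion.** The point holds in this form: the protocol combines an unmatched design with two unadjusted main analyses, so its headline figures are open to bias in either direction from age and sex. The textual fact is certain. The size and direction of the bias are not, because r, g and the sex figures are assumptions. Over the assumed range, with the same direction and no tumour effect, the crude test is significant in 12% to 97% of studies, with AUC 0.51 to 0.57.

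The documents do not support the stronger conclusion that confounding could account for the planned effect. The spurious d in that range is at most 0.24. Even with r = 0.4 and a gap of 1.5 SD it is 0.60, half of 1.2. The realistic risk is a false positive, a missed difference or a misstated size when the true effect is smaller than planned. Because a valid adjusted test is already planned, the change should be made but the flaw is not fatal.

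**What to change.** In Protocol section 5.3:

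1. Make the primary comparison a linear regression of the succinylation level (log-transformed if needed) on group, age and sex, reporting the adjusted difference and its 95% CI.
2. Report a covariate-adjusted (age- and sex-specific) ROC and AUC beside the crude ROC.
3. Keep the t-test or Mann-Whitney test and the crude ROC as supportive. The crude ROC still describes a single cut-off applied regardless of age.
4. State that the DeLong test compares age + sex with age + sex + marker.

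The cost is wording and one more regression, since age and gender are already planned covariates. The headline difference or AUC may become less favourable. The adjustment also relies on the age ranges of cases and controls overlapping, so the age and sex distributions should be shown by group. If control recruitment is still open, frequency matching on age and sex would reduce that reliance, but it is a change to recruitment and not only to wording.

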Succinylation modification, as a widely existing post-translational modification of proteins, has potential biomarker value in malignant solid tumors. Besides tumors, existing studies have shown that some diseases (such as inflammatory diseases, infectious diseases, metabolic diseases, cardiovascular diseases, neuro-psychological diseases, etc.) have certain correlations with non-histone succinylation modification. The role of histone succinylation modification in other diseases is currently lacking in relevant clinical research evidence and awaits further exploration in this study. Therefore, this research focuses on malignant solid tumors, not only filling the knowledge gap in this field but also laying the foundation for future expansion to other diseases.

2.1.2 project objective

The core objective of the project is to systematically verify and establish the clinical

application value of serum histone succinylation modification as a novel, efficient and non-invasive pan-tumor biomarker.

Objective 1: Verify the potential of pan-tumor screening: Through large-scale case-control studies, it is clearly confirmed that there are significant differences in histone succinylation levels in serum between patients with malignant solid tumors and healthy individuals, thereby providing a solid evidence-based basis for developing it into a blood-based early screening tool suitable for multiple tumor types.

Objective 2: Exploring clinical application scenarios: The project will conduct an in-depth analysis of the association between serum histone succinylation levels and different types of tumors as well as different tumor stages, and evaluate its ability to distinguish tumor types and reflect disease progression. Meanwhile, analyze its correlation with therapeutic effects (changes in levels before and after surgery, radiotherapy, and systemic treatment) and clinicopathological characteristics, and explore its application prospects in dynamic monitoring of therapeutic effects and prognosis assessment.

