Based on the findings in solid tumors, the level of histone succinylation modification in tumor tissues was significantly higher than that in adjacent tissues. Therefore, the research group, in collaboration with hospitals, collected blood samples from patients with different types of tumors and found that the succinylation modification at the H3K23 site of free nucleosome histones in the blood of tumor patients was significantly higher than that of normal people. However, the number of serum

samples from cancer patients still needs to be further expanded.

The research group previously isolated free nucleosomes from human colon cancer, gastric cancer, breast cancer, lung cancer, pancreatic cancer, multiple myeloma, liver cancer, cervical cancer, prostate cancer, ovarian cancer, esophageal cancer, cholangiocarcinoma and normal people's blood for Western blot. The results and gray-scale analysis statistics (see Figure 2) indicate that the succinylation modification of free nucleosome histone H3K23 sites in the blood of patients with different types of tumors (for specific information on different tumor types, see Figure 3) is significantly higher than that of normal people, revealing that the succinylation modification of free nucleosome histone in the blood of tumor patients may serve as a biomarker for the early diagnosis of tumors. However, at present, due to the small sample size, it is necessary to carry out this project to further expand the sample size and conduct in-depth research.

[figure not shown]

Figure 2 shows that the levels of free nucleosome histone succinylation modification in the blood of patients with different types of tumors are significantly higher than those of normal people: Enrich the free nucleosomes in the blood of tumor patients. Use histone H3K23 specific site succinylation modification and histone H3 acetylation modification antibodies to analyze the levels of histone succinylation modification and acetylation modification of free nucleosomes in the blood of different types of tumor patients by Western blot. And conduct gray-scale analysis and statistics on the Western blot results. Among them, N: normal human serum; T: Serum of cancer patients. Specific information on different types of tumors is shown in Figure 3.

Sample	Cancer patients	Sample	Controls
T1	Colon Cancer	N1	Healthy
T2	Stomach Cancer	N2	Healthy
T3	Colon Cancer	N3	Healthy
T4	Breast Cancer	N4	Healthy
T5	Breast Cancer	N5	Healthy
T6	Colon Cancer	N6	Healthy

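### Section 5.3 presents 500 per group as the result of Cohen's d = 1.2 and 10% dropout, but for the two-group comparison these inputs give about 14 to 23 per group, and no target that would give 500 is stated

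*Protocol*

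**What the plan says.** Protocol section 5.3 gives the design as "500 cases in the case group and 500 cases in the healthy control group". Its next sentence gives the basis: "The sample size was determined based on the effect size of the previous pre-experiment", with Cohen's d = 1.2 in brackets, "and considering a 10% dropout rate". The test level is 0.05. Power, sidedness and the analysis being sized are not stated.

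Two main analyses follow. The first compares succinylation levels between the groups by t-test or Mann-Whitney test and reports Cohen's d. The second estimates the AUC, a Youden cut-off, and sensitivity, specificity and predictive values with confidence intervals.

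Section 5.2.1 repeats the number for cases ("It is planned to select 500 patients with malignant solid tumors") and for controls, without a reason. Section 2.1.2, Objective 1, describes the scale only in words ("Through large-scale case-control studies"). Section 2.1.3 says of the earlier blood samples that "due to the small sample size, it is necessary to carry out this project to further expand the sample size". Neither gives a figure.

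**The concern.** A standardised difference of 1.2 is very large, and a comparison of two means at that effect needs tens of people, not hundreds. A sentence that ties 500 per group to this effect and a 10% allowance therefore looks wrong on sight.

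It matters because this is the protocol's only numerical justification for enrolling 1000 people. If it does not produce the number, a reader or an ethics committee cannot tell what 500 was chosen to achieve. The sentence also suggests that a formal calculation supports the design, while the accuracy measures that section 3.2 names as the evaluation index have no stated sizing target.

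**Working it through.** **Inputs from section 5.3.** d = 1.2, alpha = 0.05, 10% dropout, equal groups, t-test or Mann-Whitney test.

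**Assumptions.** Power (80-90%, then up to 99.99%), sidedness (two-sided, then one-sided), and main analysis 1 as the analysis being sized. Each n is rounded up, divided by 0.9 and rounded up again.

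**1. t-test.** The normal approximation is n = 2(z_alpha + z_beta)² / d².
- 80% power: 2 × (1.960 + 0.842)² / 1.44 = 10.9.
- 90% power: 2 × (1.960 + 1.282)² / 1.44 = 14.6.

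The noncentral t distribution gives 11.94 and 15.62, so 12 and 16, or **14 and 18** after dropout.

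**2. Mann-Whitney test.** Three methods, two-sided:

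| Method | Raw n, 80% / 90% | After dropout |
|---|---|---|
| t-test n × pi/3 (efficiency for normal data) | 12.51 / 16.36 | 15 / 19 |
| t-test n / 0.864 (worst-case asymptotic efficiency) | 13.82 / 18.08 | 16 / 22 |
| Noether, (z_alpha + z_beta)² / [6(P − 0.5)²], P = Phi(1.2/√2) = 0.802 | 14.35 / 19.21 | 17 / 23 |

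The range over methods is **15 to 23**.

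**3. Other settings.**
- Two-sided 99.99% power: 45.78 raw for the t-test, giving 52. The worst-case efficiency gives 59 and Noether 66.
- One-sided 80-90% power: 12-15 (t-test), 14-18 (Noether).
- Alpha of 0.000001 with 99% power (normal approximation): 73 before dropout, 82 after (73 / 0.9 = 81.1).

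None of these reproduces 500. The stated number is 28 to 36 times the t-test figure (500/18 to 500/14) and 22 to 33 times the Mann-Whitney figure (500/23 to 500/15).

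**4. What 500 per group delivers for main analysis 1.** 500 less 10% leaves 450 evaluable.
- The noncentrality at d = 1.2 is 1.2 × √(450/2) = 18.0 against a critical value of 1.96, so power is essentially 100%.
- The detectable d is about (z_alpha + z_beta) × √(2/450), which is 0.187 at 80% power and 0.216 at 90%. That is roughly one sixth of 1.2.

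**5. The route through main analysis 2.** Assume normal data with equal variance and a shift of 1.2. Then AUC = 0.802, and sensitivity and specificity at the Youden cut-off are both Phi(0.6) = 0.726.

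*AUC (Hanley-McNeil).* Variance = [A(1 − A) + (n − 1)(Q1 − A²) + (n − 1)(Q2 − A²)] / n², where Q1 = A/(2 − A) = 0.669 and Q2 = 2A²/(1 + A) = 0.714. At n = 450 this is (0.159 + 11.79 + 31.74) / 202,500, so SE = 0.0147 and the 95% half-width is 0.029.

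*Sensitivity (normal approximation, cut-off taken as fixed).* Half-width at n = 450 is 1.96 × √(0.726 × 0.274 / 450) = 0.041.

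| Assumed 95% half-width | n per group | After dropout |
|---|---|---|
| AUC 0.05 | 150 | 167 |
| AUC 0.03 | 415 | 462 |
| AUC 0.029 | 444 | 494 |
| AUC 0.025 | 597 | 664 |
| Sensitivity 0.05 | 306 | 340 |
| Sensitivity 0.041 | 455 | 506 |
| Sensitivity 0.04 | 478 | 532 |

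A number near 500 can therefore be reached from d = 1.2 and 10% dropout, but only by adding a precision target of about 0.029 for the AUC or 0.04 for sensitivity. The protocol states neither.

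**The case against.** The strongest reply is that section 5.3 gives no power and does not name the analysis being sized, so its inputs fix no unique n and cannot be contradicted. Diagnostic accuracy is a listed main analysis and the evaluation index of section 3.2, and step 5 shows that the same effect size and dropout can lead to about 500 through it.

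Part of this stands. A reader might infer that d = 1.2 cannot lead to 500 by any route, or that the accuracy analyses have no link to it. The documents do not support that. What the check shows is narrower: 500 does not follow from a calculation for the group comparison. That reading remains the natural one, because section 5.3 reports Cohen's d only in main analysis 1, and the other route needs a target found nowhere in the protocol.

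Three lesser replies:
- *The wording is a loose translation, and other considerations may have counted.* Possibly, but the sentence names two inputs and no others. If something else set the number, the sentence misreports the basis.
- *The size allows for uncertainty in the pilot.* Suppose d = 1.2 came from the 40 patients and 32 controls of Figure 3, which the protocol does not say. The standard error of d is then √(72/1280 + 1.44/144) = 0.257 and the lower 95% limit is about 0.70. That needs about 45 per group at 90% power, or 50 after dropout.
- *A SAP may explain it.* It could supply another rationale, but it would not make the group-comparison calculation give 500.

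**Conclusion.** The point holds in this form: the basis given in section 5.3, read as sizing the two-group comparison, does not yield the stated number. The discrepancy is more than twenty-fold at conventional power (14-23 against 500), and still more than seven-fold at 99.99% power (500/66 = 7.6). Power, sidedness and the target analysis are assumptions made here. The first two were varied widely without changing the conclusion. The third matters: with main analysis 2 as the target and an unstated half-width of about 0.029 (AUC) or 0.04 (sensitivity), about 500 is attainable.

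A reader might infer that the study enrols too many people. That does not follow. Accuracy, tumour type, stage and survival are also analysed, and the group comparison alone does not say how many people they need. Nor is there a power shortfall, since the group comparison has power of essentially 100% at d = 1.2. No test, estimate or enrolment figure is affected. The defect is in the stated justification, and it should be corrected.

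**What to change.** Keep 500 per group. Replace the sample-size sentence in section 5.3 so that it no longer presents 500 as the result of a d = 1.2 group-comparison calculation. The new text should:

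- name the analysis and the target that actually set 500 (for example a half-width for AUC or sensitivity, or subgroup needs), or say that feasibility set it;
- report what 450 evaluable per group delivers, with the power and sidedness used: power essentially 100% at d = 1.2, and detectable d of about 0.19 to 0.22 at two-sided 80-90% power;
- give the expected 95% half-widths for the AUC and sensitivity, about 0.029 and 0.041 under a normal shift of 1.2, with that assumption stated.

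The cost is a few lines of protocol wording, with no change to enrolment or analysis. The downside is that the sponsor may have to say that feasibility set the number.

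### The main sensitivity, specificity, PPV and NPV are in-sample values at a Youden cut-off chosen on the same 500 + 500 subjects, about 1 point too high on average; the only out-of-sample estimate is a sensitivity analysis

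*Protocol*

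**What the plan says.** Section 3.2 names the accuracy measures first among the study's indicators: "The evaluation indicators are: the sensitivity, specificity, positive predictive value, negative predictive value of the serum histone succinylation screening method". Section 5.3 then fixes how they are obtained.

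- The main analysis has two parts: a group comparison and a diagnostic evaluation. The second begins "Calculate the area under the curve (AUC) and its Bootstrap 95% CI through the ROC curve". It goes on to "determine the optimal cut-off value by maximizing the Youden index", and reports sensitivity, specificity, PPV and NPV "and their exact Clopper-Pearson 95% CI".
- The bootstrap is named only for the AUC interval. The diagnostic step has no pre-set cut-off, separate data set, cross-validation or optimism correction.
- The only training and validation step stands under sensitivity analysis: "the 70%-30% dataset was split for cutoff value training - validation".
- The multivariable part adds a conditional selection step: "If multi-site modifications are detected, LASSO regression is used to screen biomarker combinations".

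The protocol does not say in words that the cut-off and the accuracy values come from the same subjects. It follows, because the main analysis names no other data and the split is listed separately.

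**The concern.** The Youden rule picks the threshold at which sensitivity plus specificity is largest in the observed sample. It therefore exploits chance as well as signal, and accuracy scored on the same sample is too high on average. Clopper-Pearson limits are exact for a threshold fixed beforehand. Here they are centred on an inflated proportion and ignore the selection.

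At stake are the accuracy figures a reader would quote for a screening test. The errors are one-sided: when the interval misses, the truth nearly always lies below the lower limit, which is the limit used to judge whether a test is good enough.

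This is not a detail left to an analysis plan. The protocol itself fixes the cut-off rule, the estimators, the interval method and the ranking of main over sensitivity analysis.

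**Working it through.** **Inputs from section 5.3.** Group sizes are "500 cases in the case group and 500 cases in the healthy control group". Cohen's d is 1.2 from the pre-experiment, and dropout is 10%, so 500 × 0.9 = 450 per group as the smaller case. The split gives 0.7 × 500 = 350 per group for training and 0.3 × 500 = 150 for validation.

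**The plan's own figure.** The protocol states that "The sample size was determined based on the effect size of the previous pre-experiment". The usual formula n = 2(z₁₋α/₂ + z₁₋β)²/d² with two-sided α = 0.05 gives 11 per group at 80% power and 26 at 99% (13 and 29 after dropout), so 500 is not reproduced. That is a separate matter; 500 is taken here as given. The protocol states no expected accuracy to reproduce.

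**Assumption.** Controls are N(0,1) and cases N(d,1). Skewness common to both groups changes nothing, because the Youden cut-off depends only on ranks.

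**Method.** In each simulated trial the empirical Youden cut-off t was found on all subjects. The truth is the accuracy of that adopted cut-off: sensitivity 1 − Φ(t − d), specificity Φ(t). Optimism is the apparent value minus the truth. At the sample's 50% case share, PPV = se/(se + 1 − sp) and NPV = sp/(sp + 1 − se).

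**Result at d = 1.2, 500 + 500.** Over 5,000 runs:
- sensitivity: apparent 0.7307, true 0.7206, difference 1.01 points
- specificity: apparent 0.7357, true 0.7259, difference 0.98 points
- PPV and NPV: 1.00 point each; Youden index: 1.99 points

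A separate set of 6,000 runs gave 0.97 and 1.00 points for sensitivity and specificity. There the mean interval half-width was 3.9 points and sensitivity coverage 93.6%. The truth lay below the lower limit in 6.0% of runs and above the upper in 0.5%; 2.5% on each side is nominal. Reported sensitivity was below the truth in 30.4% of runs.

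**Range over assumptions** (6,000 runs each):

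| Setting | Sens. optimism (points) | Spec. optimism (points) | Sens. coverage |
|---|---|---|---|
| d = 1.2, 450 per group | 1.08 | 1.05 | 93.4% |
| d = 0.3 | 1.48 | 1.50 | 91.4% |
| d = 0.8 | 1.15 | 1.16 | 92.9% |
| d = 2.0 | 0.73 | 0.77 | 94.1% |
| case SD 1.5 times control SD | 0.90 | 0.91 | 93.7% |
| case SD 2 times control SD | 0.78 | 0.81 | 94.3% |
| half of cases unshifted, overall d = 1.0 | 0.73 | 0.72 | 94.9% |
| half of cases unshifted, overall d = 1.2 | 0.39 | 0.41 | 95.3% |

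In the last four rows specificity coverage is 93.3% to 93.8%.

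**The planned split at d = 1.2.** Bias is −0.06 points for sensitivity and 0.02 for specificity, with coverage 96.4%. The half-width is 7.4 points: for example, 109/150 gives 0.648 to 0.796, whereas 363/500 gives 0.685 to 0.765. The split also validates a cut-off trained on 350 + 350, not the one the main analysis reports.

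**Alternatives on all subjects at d = 1.2** (2,000 runs, 200 resamples):

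| Estimate of sensitivity | Bias (points) | RMSE (points) |
|---|---|---|
| apparent | 0.99 | 2.15 |
| bootstrap-corrected | 0.22 | 1.98 |
| 10-fold cross-validated | −0.04 | 2.92 |

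Clopper-Pearson limits shifted by the estimated optimism cover 95.9% for sensitivity (misses 2.4% below, 1.8% above) and 95.0% for specificity. Joint coverage is 91.1%, against 88.4% uncorrected; two independent 95% intervals would give 0.95² = 90.25%. PPV and NPV bias falls from 0.97 and 0.98 points to 0.25 and 0.22.

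**The case against.** The strongest reply is that the protocol already contains the answer. The split is planned and unbiased, nothing says it may be left unreported, and using all data first with a split for robustness is a common ordering. The bias is about a quarter of the half-width (1.0/3.9), no accuracy threshold is set that 1 point could cross, and the main purpose in section 3.1.1 is the group difference, which is unaffected. In a pan-tumour study where some tumours do not raise the marker, sensitivity optimism may be only 0.4 to 0.7 points. All of this stands and limits the weight of the point. It does not change the fact that the values ranked as main are the biased ones.

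A second reply is that shifted Clopper-Pearson limits are not exact either, and that the gain in RMSE is small. Both are true. The target, however, is the accuracy of the adopted cut-off, and for it the shifted limits covered 95.1% to 96.4% for sensitivity in the settings tested, with misses roughly balanced at d = 1.2.

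A third reply is that LASSO is conditional and outside the main step. That is right. It would add optimism if used on the same subjects, but the number of sites is not given, so no size is claimed.

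**Conclusion.** The concern holds and is minor. Followed as written, the plan reports main accuracy values that are about 1.0 point high on average for each of the four measures, with nominal 95% limits that cover sensitivity 93.6% of the time and miss almost entirely on one side. This rests on a normal, equal-variance marker at d = 1.2 with 500 per group. Over the other settings, sensitivity and specificity optimism runs from 0.4 to 1.5 points and sensitivity coverage from 91.4% to 95.3%. The PPV and NPV figures refer to the sample's 50% case share; which prevalence to use is a separate question.

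**What to change.** Keep all subjects in the main analysis and correct sensitivity, specificity and the Youden index for optimism:

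1. In each bootstrap resample, repeat the cut-off selection, and the LASSO selection if it is used.
2. Take the accuracy in the resample minus the accuracy of that same cut-off in the full data, and average over resamples.
3. Subtract this average from the apparent value and from both Clopper-Pearson limits. State that the target is the accuracy of the adopted cut-off.
4. Compute PPV and NPV from the corrected values at whatever prevalence the plan uses.
5. Label the in-sample values as apparent. Show the 70%-30% result and the 10-fold cross-validated Youden index beside them as checks. Do not attach plain Clopper-Pearson limits to the pooled fold counts: they covered only 83.3%.

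The cost is analysis wording and a little code. No subjects are added, and the resamples for the AUC interval can be reused. The reported estimates fall by roughly 1 point, about 0.2 points of bias remain, and the interval width stays at about ±3.9 points. Making the split the main result instead would widen it to about ±7.4.
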